5.1. Recruitment

Participants will be recruited from persons reporting alcohol use at their clinic visits.

a) DIPT1/2 participants will be recruited from HIV-infected persons at the Mbarara Municipal Clinic (MMC) in Mbarara, Uganda. Participants will also be recruited from the electronic medical records of persons attending the Mbarara ISS clinic. The AUDIT-C is conducted routinely at the initial clinic visit. Our prior studies showed that 64% of those reporting any alcohol use at initial clinic visit were heavy drinkers,¹⁰² thus ISS clinic patients reporting any alcohol use will be invited for further screening.

b) DIPT 2/2 participants will be recruited from HIV-infected persons at SEARCH clinics in southwestern Uganda, including newly diagnosed HIV-infected persons entering the cohort. We will invite adults in the SEARCH study who have reported any alcohol use (asked annually), as well as adults not participating in the SEARCH study but attending a SEARCH-associated HIV clinic, for further screening. Recruitment may also occur at additional HIV clinics in Southwestern Uganda as needed to meet study target enrollment.

For all sites of enrollment, a clinic staff member who is also a member of the research team, e.g. the screener, record room staff or clinic counselor, will initially approach those meeting these criteria. Persons meeting the initial eligibility criteria will be asked by the study screener or clinic staff member if they are interested in taking part in a research study. Those who agree will be screened to determine further eligibility criteria. The screener will review clinic medical records for potential participants, to determine preliminary study eligibility (i.e. age, no history of prior active TB, current drinker). Those who are eligible will be referred to the RA to undergo informed consent.

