5.2.1. Inclusion criteria

Trial inclusion criteria for all sites will be:

- a) HIV-infected adult (≥ 18 years) prescribed ART for at least 6 months;
- b) Current heavy alcohol use confirmed by urine EtG and AUDIT-C positive for prior 3-month drinking;
- c) Positive TST (≥ 5 mm induration);
- d) AST and ALT $< 2 \times$ the upper limit of normal (ULN);
- e) Fluent in Runyankole or English
- f) No history of active TB, TB treatment, or TB preventive therapy;
- g) Lives within 2-hour driving distance or 60 km of the study site.

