5.9.3. Aim 3a analyses

We will use multiple logistic regression models including variables to represent the study arms and will also adjust for gender and study site (randomization stratification factors) to improve efficiency, as in Aims 1 & 2. The 3 pairwise comparisons of primary interest are between each intervention (Arms 2, 3, and 4) vs. control (Arm 1) and we will adjust for the multiple comparisons using the Hochberg sequential test procedure.¹⁸⁵ A secondary outcome of interest is virologic suppression at trial completion, analyzed using the same approach as above.

Statistical power: We expect 15% loss to follow-up at 6 months post-trial. We assume a conservative analysis based on a Bonferroni adjustment for multiple comparisons. For an overall type I error rate of 5%, we assume each of the 3 pairwise comparisons will be conducted at an alpha level of 0.0167. We expect that 67% of participants in the control group will have viral suppression at 6 months post-trial (SEARCH data). Given this assumption, the proposed study has 80% power to detect an absolute difference of 17% in the proportions with undetectable viral load for any of the 3 comparisons of interest (e.g., 84% vs. 67% in Arms 2,3, and 4 versus Arm 1, respectively) using a chi-square test with continuity correction.

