Figure 1. Schematic of study design and aims of the Drinkers' Intervention to Prevent TB (DIPT) trial

Objectives

The DIPT trial is designed to achieve three aims. Aim 1: To determine the effectiveness of financial incentives contingent on low alcohol use (Arms 2 and 4) versus no alcohol incentives (Arms 1 and 3) to reduce heavy drinking during INH preventive therapy. The hypothesis for Aim 1 is that participants receiving incentives for negative urine EtG testing will have lower alcohol use, determined via a medium-term alcohol biomarker during INH, compared to participants receiving no alcohol incentives. Aim 2: To determine the effectiveness of financial incentives contingent on high INH adherence (Arms 3 and 4) versus no INH adherence incentives (Arms 1 and 2) to increase INH adherence during INH preventive therapy. The hypothesis for Aim 2 is that participants receiving incentives for positive POC IsoScreen testing will have better adherence to INH, determined via objective monitoring, than participants receiving no INH adherence incentives. Aim 3: To determine the effectiveness of financial incentives (Arms 2, 3, and 4) versus no financial incentives (Arm 1) on HIV virological suppression after completing their INH preventive therapy. The hypothesis for Aim 3 is that participants receiving financial incentives have higher rates of HIV virological suppression six months after INH completion.

Primary outcomes

The study has two primary outcomes. The primary outcome for Aim 1 (i.e., to estimate the effect of incentives contingent on negative urine EtG tests) is no heavy alcohol consumption over the six months of INH preventive therapy, a binary variable. This is defined as a composite outcome of both PEth <35 ng/mL and negative AUDIT-C score at both the 3- and 6-month visits. We will use standard AUDIT-C cutoffs (≥ 3 for women and ≥ 4 for men) to define heavy drinking.

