Participants who met eligibility criteria and enrolled in the study will be compared with eligible participants who declined enrollment by variables collected during screening, using the 2 independent samples t-test and Fisher's exact test.

Analyses of the primary outcomes

Primary analysis - factorial analysis. For each primary outcome, we will use a multivariable logistic regression model to estimate the effect of the relevant intervention while adjusting 1) for the other intervention and 2) the stratification randomization factors (gender and study site). We will then use the parameter estimates from this logistic regression model to predict the probability of the outcome under the intervention versus no intervention and obtain the

adjusted absolute risk (proportions with outcome value equal to 1) for intervention and no intervention, the risk difference (primary treatment effect measurement), and risk ratio with 95% confidence intervals and p-values.

The trial focuses on two distinct domains: level of drinking - with a drinking outcome and an intervention consisting of economic incentives conditional on drinking- and level of adherence - with an INH adherence outcome and an intervention consisting of economic incentives conditional on INH adherence. Each domain is conceptually different and deserves to be tested at their own 5% two-sided level of significance.

Estimation of adjusted absolute risks, risk difference and risk ratios for the drinking outcome

Let π_i be the probability of the individual i to experience the alcohol outcome, $alcohol\ int_i$ a binary indicator for whether the individual i was randomized to receive the alcohol intervention (0: arms 1 or 3; 1: arms 2 or 4), $adherence\ int_i$ a binary indicator for whether the individual i was randomized to receive the INH adherence intervention (0: arms 1 or 2; 1: arms 3 or 4), and z_i the value of the randomization stratification factor. The model will be parametrized as:

$$logit(\pi_i) = \beta_0 + \beta_1 Alcohol\ Int_i + \beta_2 Adherence\ Int_i + \beta_3 z_i$$

Given that our goal is to estimate the effect of the alcohol intervention on the alcohol outcome, we will use the parameter estimates from this logistic regression model to estimate the predicted probability of the alcohol outcome π_i for each individual i had they received the alcohol intervention:

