If for a given outcome no significant interaction between the two interventions is found, then no further action is required. If for a give outcome a significant interaction is found, then we will report the effect of the intervention stratified by levels of the other intervention. More specifically, if there is significant interaction between the alcohol and INH adherence intervention on the alcohol outcome, we will report two effects of the alcohol intervention, one for each level of the adherence intervention: 1) the effect of Arm 2 (alcohol intervention only) versus Arm 1 (control) and 2) the effect of Arm 4 (alcohol and INH adherence intervention) versus Arm 3 (INH adherence intervention only). Similarly, if there is if there is a significant interaction between the alcohol and INH adherence intervention on the INH adherence outcome, we will report two effects of the INH adherence intervention, one for each level of the alcohol intervention: 1) the effect of Arm 3 (INH adherence intervention only) versus Arm 1 (control) and 2) the effect of Arm 4 (alcohol and INH adherence intervention) versus Arm 2 (alcohol intervention only). Several conflicting viewpoints are expressed in the literature regarding the circumstances in which a multiple-testing correction should be used [5, 6]. For these analyses we choose not to adjust for multiplicity and use a 5% level of significance to test the effect of the intervention, while explicitly reporting a priori the comparisons that will be made.

Missing data: The primary statistical analyses will consist of a complete case analysis of individuals with non-missing outcomes. However, participants who miss the 3-month or/and 6-month visit will have missing data on the drinking outcome, which requires PEth measurements and AUDIT-C at both 3 and 6 months. To examine potential missing data mechanisms, we will compare the characteristics of the individuals who had complete data and missing data on the outcome. To examine the robustness of our findings, we will conduct a sensitivity analysis conservatively assuming that individuals who missed a study visit at 3 and/or 6 months were drinking heavily (alcohol outcome). This assumption is reasonable in this population of heavy drinkers. Finally, if it is reasonable to assume that data are missing at random and the proportion of missing data is more than 10%, we will consider using inverse probability weighting to impute the missing outcomes.

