Analyses of the secondary outcomes

For the hepatotoxicity outcome, we will use a logistic regression model including indicator variables to represent the study arms and, to improve efficiency, the randomization stratification factors (gender and study site). We will conduct 3 pairwise comparisons between each intervention (Arms 2, 3, and 4) versus the control (Arm 1).

For all other binary secondary outcomes, we will use the same statistical approach we described for the primary outcomes including a factorial analysis and a test for interaction between the interventions.

If the statistical analyses indicate an effect of the alcohol intervention versus no alcohol intervention on HIV virological suppression, we will then conduct a mediation analysis to explore the role of alcohol drinking as a potential mediator that may drive the intervention to improve HIV virologic suppression. Similarly, if the statistical analyses indicate an effect of the INH adherence intervention versus no INH adherence intervention on HIV virological suppression, we will then conduct a mediation analysis to explore the role of INH adherence as a potential mediator that may drive the intervention to improve HIV virologic suppression. More specifically, we will use methods for mediation analysis to derive the direct and indirect effects of the incentives for the primary outcomes while allowing for exposure-mediator interactions[7, 8]. We will specify a priori the list of mediator-outcome confounders.

For all continuous secondary outcomes, we will fit linear regression models. We will explore transformations for variables that are not normally distributed. If an appropriate transformation is not identified, median regression will be used. For the continuous alcohol outcomes, we will also adjust the models for the baseline drinking variables (analysis of covariance).

For all secondary outcomes, we will declare statistical significance if the p-value is < 0.05.

Missing data. For all secondary analyses we will conduct a complete case analysis.

Exploratory analyses

Exploratory outcomes. Exploratory outcomes for Aim 1 are the following continuous measures of drinking: 1) self-reported number of drinking days in the prior 30 days, 2) number of heavy drinking days (defined as ≥ 4 drinks/occasion and ≥ 5 drinks/occasion for women and men, respectively) in the prior 14 days, and 3) PEth as a continuous variable measured at other time points.

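### Free precision gain, not an error: the SAP's binary models for Aim 1 drinking and for viral suppression leave out baseline PEth, AUDIT-C and viral load, which the trial collects

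*SAP*

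**What the plan says.** **Covariates.** Under Analyses of the primary outcomes, the SAP fits a logistic model for each primary outcome "while adjusting 1) for the other intervention and 2) the stratification randomization factors (gender and study site"). It then averages predicted probabilities over the sample to obtain a standardised risk difference, which is the main effect measure. Under Analyses of the secondary outcomes it states: "For all other binary secondary outcomes, we will use the same statistical approach we described for the primary outcomes". Hepatotoxicity is the exception, so the rule covers viral suppression at months 6 and 12.

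**Outcome and analysis set.** The Aim 1 outcome is a "composite outcome of both PEth <35 ng/mL and negative AUDIT-C score at both the 3- and 6-month visits". On missing data, the SAP says: "The primary statistical analyses will consist of a complete case analysis of individuals with non-missing outcomes".

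**Where baseline drinking is used.** "For the continuous alcohol outcomes, we will also adjust the models for the baseline drinking variables (analysis of covariance"). It also appears as a potential effect modifier under Subgroup analyses.

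**What is collected.** Protocol Table 2 schedules viral load at eligibility, and PEth and the study interview at baseline. Table 3 lists AUDIT-C at baseline. Protocol 5.7.2 names baseline alcohol use and viral suppression as covariates, but for describing the population and as possible confounders.

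**Imbalance rule.** Protocol 5.9 adds to adjusted analyses any baseline covariate found to differ between arms, and 5.9.1 and 5.9.2 put unbalanced confounders into the primary models. The SAP does not carry this forward, and says that arm differences will not be judged by significance.

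**The concern.** A baseline measurement of the outcome, or of something close to it, is usually among the strongest predictors of that outcome. Adjusting for it removes variance that randomisation leaves in the comparison. The SAP accepts this for continuous alcohol outcomes but not for the binary ones, although the data are already in hand. At stake is the width of the confidence intervals for the Aim 1 primary outcome and for viral suppression, which the protocol made the Aim 3 primary outcome and the SAP treats as secondary. Two different covariate rules in the two documents also leave room for a choice made after the data are seen.

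**Working it through.** **1. The plan's own power figures.** Aim 1 (protocol 5.9.1): 612 evaluable, 306 v 306 at the factorial margin, 15% v 25%, two-sided 0.05, continuity-corrected chi-square.

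- Continuity-corrected size: n0 = (n·d − 1)² / (n·d²) = (30.6 − 1)² / 3.06 = 286.3 per group.
- z = [d√n0 − 1.96√(2p̄(1−p̄))] / √(p1q1 + p2q2) = (1.692 − 1.109) / 0.561 = 1.04, so power is 85.1%. Exact enumeration of the corrected test gives 85.3%. The stated 80% is therefore conservative.
- Aim 3a (protocol 5.9.3): 144 per arm, alpha 0.0167, 67% v 84%, gives 80.0%. This reproduces.

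**2. Is the planned model valid?** The SAP's estimator was simulated without the baseline covariate. Bias of the risk difference was at most about 0.002, coverage of the 95% interval 94-96%, and type I error 4.3%. With the covariate added, the mean risk difference was essentially unchanged. The standardised risk difference is marginal, so the target stays the same.

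**3. Aim 1: size of the loss (all correlations assumed).** PEth and AUDIT-C were simulated as latent normal variables at baseline, month 3 and month 6. The month 3 to month 6 correlation was 0.7, the same-visit PEth to AUDIT-C correlation 0.5, and the baseline-to-follow-up correlation r. Success means all four follow-up values fall below a threshold set to give 15% or 25%. Entry was represented by removing the lowest 25% or 36% of baseline values. The 36% is the complement of protocol 5.1's figure that "64% of those reporting any alcohol use at initial clinic visit were heavy drinkers". Cut in the variance of the risk difference against the planned model:

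| Entry removes the low end of | r | PEth alone | PEth + AUDIT-C |
|---|---|---|---|
| AUDIT-C and PEth | 0.3-0.6 | 1-7% | 2-11% |
| AUDIT-C only | 0.3-0.6 | 2-9% | 3-13% |
| AUDIT-C only | 0.7 | 11-13% | 17-20% |

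The second and third rows are closer to the documents. Entry requires "Current heavy alcohol use confirmed by urine EtG and AUDIT-C positive for prior 3-month drinking", and there is no PEth criterion, so PEth is narrowed only through its association with AUDIT-C and EtG.

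In practical terms, the unadjusted 95% half-width is 1.96√[(0.1275 + 0.1875)/306] = 6.29 points. Multiplying by √(1 − cut), a 1% cut gives 6.26 and a 13% cut gives 5.87. Dividing n0 by (1 − cut) moves power from 85.1% to about 85.4% and 89.6%.

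**4. Viral suppression: size of the loss (baseline association assumed).** Protocol 5.9.3 supplies the rate: "We expect that 67% of participants in the control group will have viral suppression at 6 months post-trial". With 15% loss, 680 × 0.85 = 578, or 289 v 289 in the SAP's factorial comparison at alpha 0.05.

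- For a yes/no baseline covariate, R² = p(1−p)·gap² / [m(1−m)]. Here p is the share suppressed at baseline, m the share at month 12, and gap the difference in month-12 suppression between participants suppressed and not suppressed at baseline. If p = m, R² = gap². Gaps of 30, 40 and 50 points give 0.09, 0.16 and 0.25.
- Simulating the SAP's estimator (n = 578, p = m = 0.67, effect +10 points) gives variance cuts of 8%, 15% and 24%. The half-width falls from 7.26 points to 6.95, 6.70 and 6.35.
- The difference detectable with 80% power from 67% falls from 10.7 points to 10.2 at R² = 0.10 (gap 32 points) and 9.7 at R² = 0.20 (gap 45 points). From 81%, the SEARCH figure in protocol 3.1, it falls from 8.6 to 8.2 and 7.8.

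**5. Is the order of the two gains fixed?** A simpler model gave both outcomes the same latent baseline-to-outcome correlation of 0.5. R² was 0.13 for Aim 1 with an unrestricted drinking range, 0.06 if the least-drinking 30% are removed at entry (an assumed share), and 0.09-0.10 for viral suppression. The order depends on how far entry narrows baseline drinking, which the documents do not quantify.

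**The case against.** Pre-specified adjustment for the stratification factors with a standardised risk difference is an accepted choice, and nothing about it is wrong. The Aim 1 comparison exceeds its target power without help. Viral suppression is secondary in the SAP. Baseline drinking is already used for continuous PEth and in the subgroup models. The change is not quite free: it needs a functional form, a rule for missing baseline values and a retained sensitivity model. The SAP is dated August 2022 and recruitment began in April 2018, so its value depends on whether outcomes have been seen. All of this stands, and it limits the priority; it does not remove the gain.

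Three stronger readings are tempting, and the documents do not support them.

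- **That the omission biases the result.** It does not; see step 2.
- **That the gain is known to be small for Aim 1 and larger for viral suppression.** Neither document gives the baseline-to-outcome association for either outcome, and the ranges of 1-13% and 8-24% overlap.
- **That entry restricts baseline PEth as it restricts AUDIT-C.** The criteria act on AUDIT-C and urine EtG. The 64% figure describes heavy drinkers among clinic patients reporting alcohol use and sets no PEth limit.

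On the other side, viral load is not an entry criterion, but at least six months of prescribed ART is, and that may narrow baseline suppression indirectly. The 81% is a cohort figure, not one for heavy drinkers.

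**Conclusion.** The binary models leave out prognostic baseline measures that the trial collects. The cost is precision only. The plausible cut in variance is about 1-13% for Aim 1 (r = 0.3-0.6; more at higher r) and about 8-24% for viral suppression (gaps of 30-50 points). These figures rest on assumed correlations and gaps, and for Aim 1 also on an assumed effect of eligibility. A larger gain for viral suppression is plausible, because baseline status repeats the same measure, but it is not established.

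One benefit needs no assumed correlation: a fixed covariate list would settle the difference between the protocol's imbalance-triggered rule and the SAP. Priority is optional and low for Aim 1, and modest for viral suppression.

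**What to change.** Before unblinded outcomes are seen, amend the SAP to:

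1. Add baseline viral suppression (yes/no) to the month-6 and month-12 suppression models.
2. Add baseline log PEth to the Aim 1 primary logistic model, with AUDIT-C score as an optional second covariate. A yes/no baseline AUDIT-C status would add nothing, because entry requires it to be positive.
3. Keep the standardised risk difference as the effect measure.
4. State one simple rule for missing baseline values, for example a single value imputed from the pooled arms, so that the complete-case analysis loses no further participants.
5. Keep the model with stratification factors only as a sensitivity analysis.
6. State that this fixed list replaces the imbalance-triggered adjustment in protocol 5.9 to 5.9.2.

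If outcomes are already unblinded, keep the planned model as primary and report the adjusted model as the sensitivity analysis.

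The cost is a few lines of SAP text, with no new data and no change in what is estimated.

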The primary outcome for Aim 2 (i.e., to estimate the effect of incentives contingent on a positive IsoScreen test) will be INH adherence measured as >90% pill-taking days by MEMS cap opening during the six-month course of INH or the time prescribed for those who were instructed to discontinue INH, a binary variable. The participants were given up to 9 months to complete a 6-month (180-pill) INH preventive therapy course. Therefore, MEMS adherence is defined as the number of pill bottle openings (no more than 1 per day counted) within a 270-day window divided by the number of prescribed doses (180, unless the participant discontinued the medication).

The outcome for Aim 3 is treated as a secondary outcome (see below).

Secondary outcomes

The secondary outcome for Aim 1 is PEth as a continuous variable measured at the 6-month visit.

The secondary outcome for Aim 2 is MEMS-measured adherence as a continuous variable (defined as the proportion of days with a bottle opening out of number of days prescribed within 9 months of randomization).

The outcome of Aim 3 is HIV virological suppression defined as an undetectable plasma HIV viral load at the 12-month visit (a binary variable). Another secondary outcome for Aim 3 will be HIV virological suppression at the 6-month visit (a binary variable).

Another secondary outcome is INH preventive therapy discontinuation due to grade 3 or grade 4 hepatotoxicity at any time while receiving INH (a binary outcome). Grade 3 hepatotoxicity was defined as AST or ALT ≥ 5 ULN or based on symptoms that met pre-specified Grade 3 criteria for hepatotoxicity. Grade 4 hepatotoxicity was defined as AST or ALT ≥ 10 ULN or based on symptoms that met pre-specified Grade 4 criteria for hepatotoxicity.

Finally, active TB during the 12 months of follow-up (a binary outcome) is also a secondary outcome. Active TB is defined as confirmed (if Xpert MTB/RIF assay positive) or suspected (based on chest x-ray findings or response to anti-TB treatment in a symptomatic and Xpert assay negative person).

Descriptive statistics

We will report the distribution of baseline covariates overall and by randomization arm. For continuous variables, we will provide the median, mean, standard deviation, 0th, 25th, 50th, 75th, and 100th percentiles. For categorical variables, we will provide frequencies and proportions. Differences between arms will not be evaluated based on statistical significance.

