An exploratory outcome for Aim 2 will be drug concentration (ng/mg) in a subset of small hair samples. Hair levels of INH measure long-term and cumulative exposure to INH will be used to determine if short-term increases in adherence translate to sustained changes in behavior.

Intervention-by-time-interaction. For Aims 1 and 2, we will check for the presence of intervention-by-time interaction by conducting separate analyses at months 3 and 6. We will use generalized estimating equations with an independent working correlation matrix for binary outcomes and random effect models for continuous outcomes.

Impact of COVID-related disruptions. Recruitment started on April 16 2018 and study activities were paused in March 19, 2020 due to a lockdown enforced by the Ugandan government in response to the COVID-19 pandemic. During this time, all research activities were stopped and participants on INH were contacted and instructed to stop taking their INH pills immediately, as there were no means to effectively monitor for liver toxicity. Study visits resumed on May 26, 2020 and enrollment resumed on June 16, 2020. We will conduct several descriptive statistics to examine to what extent the lockdown and the pandemic might have impacted the generalizability of the trial's findings. First, we will group the participants based on whether their scheduled INH completion date was before versus on or after March 19 2020 and will compare their baseline characteristics including measures of drinking. Second, we will perform an analysis to explore whether completion of INH before or after pandemic interruption acts as potential effect modifier of the incentive interventions.

Subgroup analyses. We will perform analyses to explore potential effect modifiers of the incentive interventions. For Aims 1 and 2, the potential moderators of interest are: sex, baseline level of alcohol use, time and risk preferences, and readiness to change . For each aim, we will fit separate models including 2-way interactions between randomization group and each potential effect moderator, as well as a model testing the interaction between the two

interventions. If an interaction is significant, subsequent stratified analyses will be conducted to explore the effect of the economic incentive interventions by categories of the moderator.

References

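### Aim 1: the primary complete-case rule leaves out participants whose composite outcome is already settled as failure by the one visit they attended

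*SAP*

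**What the plan says.** The SAP (Primary outcomes) defines the Aim 1 outcome as a "composite outcome of both PEth <35 ng/mL and negative AUDIT-C score at both the 3- and 6-month visits". In the Missing data paragraph of Analyses of the primary outcomes, it makes the primary analysis a "complete case analysis of individuals with non-missing outcomes" and states that "participants who miss the 3-month or/and 6-month visit will have missing data on the drinking outcome".

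The same paragraph adds three things:
- a comparison of participants with and without the outcome;
- a sensitivity analysis "conservatively assuming that individuals who missed a study visit at 3 and/or 6 months were drinking heavily";
- possible inverse probability weighting, if missing at random is judged reasonable and "the proportion of missing data is more than 10" per cent.

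The primary effect measure is the risk difference.

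Protocol 5.9 describes an intent-to-treat analysis of everyone randomised. Protocol 5.9.5 names multiple imputation, if needed, under missing at random. Protocol 5.9.1 plans for 612 of 680 participants with both visits.

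**The concern.** Success needs every component to pass at both visits; failure needs only one to fail. A participant with a high PEth or a positive AUDIT-C at month 3 has failed the composite, whatever month 6 would have shown. The SAP nevertheless calls that outcome missing if month 6 is missed, and the same holds with the visits reversed. No passage restores these participants to the primary analysis.

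Their attended visit can still be used elsewhere. It can enter the exploratory check made by "conducting separate analyses at months 3 and 6" and, if it is month 6, the secondary outcome "PEth as a continuous variable measured at the 6-month visit". Neither of these is the primary composite.

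At stake is the risk difference for one of the two primary outcomes. If heavy drinkers are likelier to miss a visit, complete case removes failures selectively. Equal dependence in both groups leaves a true null unbiased but shifts a real effect. Unequal dependence can shift either, in either direction.

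**Working it through.** **The plan's own figures.** 680 × 0.90 = 612, so 68 are expected to lack a visit, and 306 per group remain at the Aim 1 margin. At 15% v 25% the continuity-corrected power is 85.1%, against a stated 80%. The detectable difference is 9.3 points, which the plan appears to round up to 10. This is on the safe side and does not affect the point.

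**Inputs.** From Protocol 5.9.1: 15% without and 25% with alcohol incentives, a true difference of 10.0 points. All else is assumed. Let *a* be the proportion non-heavy at month 3 and *b* the proportion non-heavy at month 6 given non-heavy at month 3.
- No alcohol incentive: a = 0.25, b = 0.60, ab = 0.15.
- Alcohol incentive: a = 0.38, b = 0.658, ab = 0.25.

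Everyone attends month 3. Month 6 is missed with probability dn (month-3 non-heavy) or dh (month-3 heavy).

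**Formulas.**
- Complete case = ab(1−dn) / [a(1−dn) + (1−a)(1−dh)]
- Missing = heavy: ab(1−dn)
- Proposed fix (month 6 imputed only for month-3 non-heavy) = ab

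Worked example, with 15% loss in month-3 heavy drinkers without the incentive and 5% elsewhere: 0.1425/0.875 = 0.1629 v 0.2500, a difference of 8.7 points. Reversed: 0.2375/0.888 = 0.2675 v 0.1500, or 11.7 points.

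For loss driven by month-6 status (ln non-heavy, lh heavy), the probability of being non-heavy at month 6 after heavy drinking at month 3 is set at 0.10. The fix becomes a × b(1−ln) / [b(1−ln) + (1−b)(1−lh)].

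| Assumed loss of month 6 | Complete case | Missing = heavy | Fix |
|---|---|---|---|
| 10% of everyone | 10.0 | 9.0 | 10.0 |
| Month-3 heavy 12%, others 4%, both groups | 10.4 | 9.6 | 10.0 |
| Month-3 heavy 15% without v 5% with incentive, others 5% | 8.7 | 9.5 | 10.0 |
| The reverse | 11.7 | 9.5 | 10.0 |
| 10%, except 2% of incentive-group non-heavy | 11.3 | 11.0 | 10.0 |
| Month-6 heavy 12%, others 4%, both groups | 10.5 | 9.6 | 10.2 |
| Month-6 heavy 15% without v 5% with incentive, others 5% | 8.7 | 9.5 | 9.3 |
| The reverse | 12.0 | 9.5 | 10.9 |

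Under a true null (15% in both groups), the 15% v 5% month-3 pattern moves complete case by about 1.3 points: 0.1629 − 0.1500.

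**Scale.** The standard error is √[(0.15×0.85 + 0.25×0.75)/306] = 0.032, or 0.029 at the null. Every shift above is smaller. With uniform loss, the simulated SD is 3.22 points for complete case and 3.14 for the fix, a ratio of 1.025.

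**If some of those lost miss both visits.** Let *s* be the share of those lost who were seen at month 3. Keep the same dependence on drinking, and assume baseline data predict nothing. The fix then replaces *a* by a(1−dn+s·dn) / [a(1−dn+s·dn) + (1−a)(1−dh+s·dh)].

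| Pattern | Complete case | Fix, s = 0.5 | Fix, s = 0.25 |
|---|---|---|---|
| 12% v 4%, both groups | 10.4 | 10.2 | 10.3 |
| 15% v 5% | 8.7 | 9.4 | 9.1 |
| The reverse | 11.7 | 10.8 | 11.3 |
| 10%, except 2% | 11.3 | 10.6 | 11.0 |

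**How many known failures.** The logical range is 0 (all 68 miss both visits) to 68. If loss is unrelated to drinking, 68 × s × (0.75 + 0.62)/2 gives about 12, 23 or 47 for s = 0.25, 0.5 or 1.

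**The case against.** An attendance rule treats successes and failures alike, whereas one visit can prove a failure but never a success. Complete case is exact under uniform loss. Simply adding back known failures is not: with 10% uniform loss it gives 0.135/0.975 = 13.8% v 0.225/0.962 = 23.4%. This stands. The repair needs an imputation model, and preferring that to complete case is partly a matter of judgement.

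The plan also has safeguards. Missing = heavy scores every known failure correctly. However, it also fails those who passed their one visit or missed both, it is only a sensitivity analysis, and it is not always conservative. At 15% v 25% it overstates the effect once loss among would-be successes without the incentive exceeds 25/15 = 1.67 times that with it.

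Weights built on the attended visit would remove the bias in the month-3 patterns above. But the SAP gives no weight model and will only consider weighting above 10% missing. The protocol plans for exactly 10%, and those dependent patterns total about 8% to 9.5%. Travel payments, calls and home visits in all arms, and rescheduling of missed visits (Protocol 5.5), also limit loss.

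A reader might infer that the primary result will favour the incentives. The documents do not support that: they give no loss by arm, and the COVID-19 pause applied to all arms. Nor may one infer that the fix is unbiased in general. Its 10.0 in the month-3 patterns depends on everyone attending month 3.

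**Conclusion.** The exclusion of observed failures follows from the SAP's own definition and rule, with no assumption needed. Its consequence is uncertain and probably small: avoidable loss of information, with possible bias if missing a visit is related to drinking. Size and direction cannot be determined from the documents. The month-3 rates and loss patterns are assumed; under them every shift is below one standard error. In the dependent-loss patterns modelled, the fix is closer to the truth than complete case, but its advantage shrinks as the share missing both visits rises. Minor.

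**What to change.** In the Aim 1 primary analysis, include all randomised participants. Score any observed PEth of at least 35 ng/mL or positive AUDIT-C at month 3 or 6 as failure. Multiply impute only the undetermined components from baseline drinking, the attended visit, both intervention factors, gender and site, then derive the composite. Do not add back known failures while dropping those who passed their only visit. Keep complete case and missing = heavy as sensitivity analyses, and report known failures and undetermined cases by arm.

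The cost is SAP wording and some programming, with no new data. The downside is reliance on missing at random for the undetermined cases. Residual bias remains if loss follows month-6 relapse (up to about 0.9 points as modelled). It also remains if participants miss both visits for drinking-related reasons that baseline data do not predict (9.1 to 11.3 points against a true 10.0 when only a quarter of those lost were seen once).
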